2 HYPOTHESIS, OBJECTIVES, AND ENDPOINTS

Jak2-Stat5 signaling pathway sustains the expression of androgen receptor (AR) and AR variants (AR-Vs) in PC cells. Inhibition of Jak2-Stat5 signaling depletes expression of AR and AR-Vs in PC cell lines, in xenograft tumors grown in nude mice and in patient-derived clinical PCs grown in tumor explant cultures *ex vivo*. We hypothesize that pacritinib through inhibition of the JAK2-STAT 5 signaling pathway would induce biochemical responses in men with systemic PC by depleting expression of AR and AR-V.

2.1 Primary Objectives

To establish the effect of pacritinib on the time to PSA progression in patients with biochemical relapse of prostate cancer by assessing the length of time that a given subject will be alive and free from PSA progression.

2.2 Secondary Objectives

1. To evaluate the absolute PSA nadir as a result of treatment which is expressed for each subject in the absolute value and as a percentage, change from baseline.
2. To determine the time to PSA nadir from the start of treatment. which is the lowest PSA on treatment.
3. To determine the time to next subsequent antineoplastic therapy.
4. To determine the effect of investigational treatment on testosterone levels which is assessed by the change of testosterone from baseline to cycle 4.
5. To determine the safety and toxicities of the study drug as assessed by CTCAE version 5.

2.3 Exploratory Objectives

1. To determine if the study drug affects comprehensive geriatric assessment domains.
2. To determine if the study drug combination affects the quality of life.
3. To evaluate if positive status for Stat5 activation in the paraffin-embedded tissue sections of the diagnostic biopsies has a trend to predict biochemical response to pacritinib treatment.

2.4 Primary Endpoint

Six-month PSA-progression free survival

2.5 Secondary Endpoint(s)

1. Absolute PSA nadir.
2. Time to PSA nadir.
3. Time to next subsequent antineoplastic therapy.
4. Effect of investigational treatment on testosterone levels.
5. Safety and toxicities of the study drug.

2.6 Exploratory Endpoints

1. Effect of pacritinib on CGA domains.
2. Effect of pacritinib on FACT-P score.
3. Effect of levels of Stat5 transcription factors in prostate cancer cells determined by fluorescence-based immunohistochemistry on biochemical responses response to pacritinib.
4. Identify biomarkers of response/resistance.

3 STUDY DESIGN

3.1 General Description

This is a single-arm, open-label phase 2 study to evaluate the role of pacritinib for patients with biochemical relapse after definitive treatment for prostate cancer. Patients will receive pacritinib 200 mg twice daily. To be eligible, patients are not allowed to have been treated with a JAK2

inhibitor. Assigned treatment will continue until the patient experiences progressive disease or intolerable adverse events (AEs), withdraws consent, initiates new PC-directed therapy, or the study is terminated. In addition to the above, patients will be considered to have discontinued treatment if pacritinib is held for >28 consecutive days due to treatment toxicity, or if treatment is discontinued for lack of efficacy, or at the request of the principal investigator or the patient. This study will be monitored by an Independent Data Monitoring Committee (IDMC).

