4.6 Discontinuation of Study Treatment, Withdrawal, and Compliance

Treatment duration is 2 years. Patients may continue drug beyond two years if, in the opinion of the treating physician, the patient is benefitting from treatment and benefits outweigh any risks of therapy

Discontinuation from the study treatment does not mean discontinuation from the study. The subject will be considered in follow-up, study procedures should still be completed as indicated by the study protocol, and AEs/SAEs will continue to be reported according to this protocol.

In the absence of treatment delays due to adverse events, study treatment/intervention may continue until:

- Disease progression per PCWG3 guidelines
- General or specific changes in the subject's condition renders the subject unacceptable for further treatment in the investigator's judgment.
- An inter-current illness that prevents further treatment administration.
- The subject decides to withdraw from the study.
- The subject has significant noncompliance with the protocol (see below).
- Unacceptable adverse event(s) and/or dose level reduction beyond requirements as detailed in this protocol.
- The clinical need for concomitant therapy that is not permitted in the study.
- Subjects who sign the informed consent form, enroll and receive the study intervention, but subsequently withdraw, or are withdrawn or discontinued from the study will not be replaced.

Progression of disease

Progression of disease per PCWG3 is defined as one or more of the following:

PSA progression

Recognize that a favorable effect on PSA may be delayed for \geq 12 weeks, even for a cytotoxic drug. Monitor PSA by cycle but plan to continue through early rises for a minimum of 12 weeks unless other evidence of progression.

If there is a decline in PSA from baseline: record time from baseline to the first PSA increase that is $\geq 25\%$ and ≥ 2 ng/mL above the nadir, and which is confirmed by a second value ≥ 3 weeks later (i.e., a confirmed rising trend).

If there is no decline in PSA from baseline but stable PSA at 12 weeks: PSA progression will be defined as $\geq 25\%$ and ≥ 2 ng/mL from PSA at 12 weeks .

Radiographic progression

Radiographic progression will be assessed per RECIST 1.1. Any new unequivocal bone lesion is considered progression, except if that lesion appears in the first post-treatment scan; in that

case, document the event, continue treatment until two additional new lesions appear, and record both events.

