8.2 Study hypotheses

The null hypothesis that the median PSA-progression-free survival is six months will be tested against a one-sided alternative by for the six-month PSA-progression-free survival probability exceeding 50%. The study is designed to have 80% power to obtain a result significant at a one-sided 10% level if the experimental treatment has a six-month PSA-progression-free probability of 66%, which corresponds to a median of 10 months if the time to PSA progression is exponentially distributed.(84)

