8.4 Analysis of primary endpoint

The probability of PSA-progression-free survival over time will be estimated using the Kaplan-Meier method and shown with 80% pointwise confidence limits. The six-month PSA-progression-free survival will be compared to the null-value of 50% using a z-test at a one-sided 10% significance level.

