8.10 Missing data

For all outcomes, summary statistics will include the count of missing and non-missing values. Patients with missing value for the primary outcome, PFS, will be censored at the time when last known to be alive and without progression. A similar approach will be used for other time-to-event outcomes, such as time to PSA nadir. Secondary outcomes requiring numeric values, such as geriatric assessments, PSA and testosterone levels will be analyzed among patients with non-missing values as required for each analysis (e.g., non-missing value at specific time point for cross-sectional analysis, and non-missing values at two time points for change analyses). The limitations of extensive missingness, if present, will be clearly noted in all reports and any related findings will be interpreted with caution.

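### The plan does not say how the primary analysis scores men stopped for lack of efficacy, or started on new therapy, before PSA progression; sparse PSA visits after treatment can leave their six-month status unresolved and bias the Kaplan-Meier tests upward

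*Combined protocol and SAP*

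**What the plan says.** Section 3.1 ends treatment for progressive disease, intolerable adverse events, withdrawn consent or new prostate-cancer therapy. It then adds further grounds on which a patient counts as having stopped: a toxicity hold beyond 28 days, "or if treatment is discontinued for lack of efficacy, or at the request of the principal investigator or the patient".

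The list in 4.6 starts with "Disease progression per PCWG3 guidelines" and does not mention lack of efficacy. The same section says that stopping treatment is not leaving the study and that study procedures continue. It plans treatment through early PSA rises for at least 12 weeks unless there is other evidence of progression. PSA progression after a decline needs a rise of at least 25% and 2 ng/mL above nadir, confirmed at least 3 weeks later. With no decline but a stable PSA at 12 weeks, the same thresholds apply from the 12-week value.

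The study calendar has an end-of-treatment visit 30 days (±7) after the last dose, then follow-up every six months (±21 days) for two years. The extracted table appears to mark PSA at both.

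Under 8.10, patients with a missing primary outcome "will be censored at the time when last known to be alive and without progression". Under 8.4, "The six-month PSA-progression-free survival will be compared to the null-value of 50% using a z-test" at a one-sided 10% level. Section 8.9 applies a Kaplan-Meier z-test against 66% for futility. Section 8.3 rejects on a count: 27 or more of 46 alive without PSA progression at six months.

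**The concern.** A man can be judged to have failed the drug before he meets the PSA rule. The path is plausible. The rule needs an absolute rise of 2 ng/mL, while entry needs a PSA of only more than 0.5 ng/mL. A man whose PSA never falls and is rising rather than stable at week 12 fits neither written definition. The study is open-label, and stopping is partly at the investigator's discretion.

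Kaplan-Meier assumes that a censored man has the same later risk as those still followed. A man stopped because the drug is not working probably has a higher risk. If his progression is not seen, the six-month estimate is too high. An inactive drug then passes the futility look more easily and reaches significance at the end more often. The 8.3 count treats the same man differently: once censored, he is not among those known to be progression-free.

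**Working it through.** **1. The plan's own figures.** Section 8.2 states: "The study is designed to have 80% power" and "to obtain a result significant at a one-sided 10% level". The null six-month value is 50%; the alternative is 66%.

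- Futility stop under the null (4 or fewer of 10): 386/1024 = 37.7%, against the stated 38%. The modified rule at 1.5 men a month gives 45.0-45.5%, against 45%. Both reproduce.
- Exact two-stage rule with 27 of 46: type I error 13.3%, power 83.1%. With 28: 8.3% and 77.2%. Neither matches 10% and 80%; that is a separate point.
- The 8.4 z-test without censoring, with p = k/46 and z = (p − 0.5)/√(p(1−p)/46). At 27: 0.0870/0.0726 = 1.20. At 28: 0.1087/0.0720 = 1.51. The critical value is 1.28, so the test needs 28, and its baseline type I error is about 8%.

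**2. When status can go unresolved.** Take a last dose at month s. The end-of-treatment visit is near s + 1 and the next visit near s + 7. For s below 5, no PSA is scheduled between month s + 1 and the landmark, a gap of 5 − s months (two months for s = 3, one for s = 4). For s between 5 and 6, the end-of-treatment visit falls at or after month 6. In every case the next visit is past month 6, and it is also the first scheduled chance to confirm a rise seen at end of treatment.

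**3. Effect on the estimate.** Let f be the share of six-month progressors whose progression goes unobserved. The documents give no f, so it is an assumption. Under the null, 23 of 46 men are expected to progress by month 6, so 23f are affected. If they are censored just before progression, the observed hazard is (1 − f) times the true one, and Kaplan-Meier at month 6 tends to 0.5^(1−f). The null standard error is √(0.25/46) = 0.0737. At f = 20% the expected z therefore shifts by 0.074/0.0737 = 1.0, against the 1.28 needed.

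**4. Simulation.** 46 men, exponential times, true six-month value 50%, Greenwood z-tests at both looks, affected men censored at various times before progression.

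| f | Men affected | 0.5^(1−f) | Null rejection, 8.4 | Futility stop, 10-man look | Futility stop, modified look |
|---|---|---|---|---|---|
| 0 | 0 | 0.500 | about 8% | 38% | 45% |
| 5% | 1.2 | 0.518 | about 13% | 33-34% | 41% |
| 10% | 2.3 | 0.536 | 17-19% | 29-30% | 36% |
| 20% | 4.6 | 0.574 | 29-35% | 21-23% | 27% |

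Where progression comes two months after the stop, further runs gave 12-17% (f = 10%) and 17-29% (f = 20%). Progression captured by the end-of-treatment PSA adds no inflation. Scoring the stops as failures returned rejection to about 8%.

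**5. Progression dated after the landmark.** These men then count as progression-free at month 6, with probability 0.5 + 0.5f. With 28 needed (the z-test without censoring), exact rejection is 14.7%, 23.7% and 47.9% for f = 5%, 10% and 20%. On this path the 8.3 count would credit them too.

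**6. How large f can be.** If no stop comes before 12 weeks (2.76 months), the end-of-treatment visit is no earlier than about month 3.75. Under the null exponential, the share of six-month progressors who progress after that is (0.5^(3.75/6) − 0.5)/0.5 = (0.648 − 0.5)/0.5, about 30%. Then f = 5%, 10% and 20% need about 17%, 34% and 67% of those men to be affected. The top of the range is demanding; the bottom is not.

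**The case against.** A reader might infer that 8.10 automatically censors every man stopped for lack of efficacy, so the primary test must reject too often. The documents do not say that. The trigger in 8.10 is a missing primary outcome, not stopping treatment, and 4.6 keeps the man in follow-up. A man stopped one month before progression may have a qualifying PSA at the end-of-treatment visit. If it is later confirmed, 4.6 dates progression to that first rise. One run that counted this PSA, for stops one month before progression, cut rejection from 18% to 13% at f = 10% and from 32% to 19% at f = 20%. All of this stands, and it makes the inflation conditional.

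Single-trial illustrations are also fragile. With 26 of 46 progression-free, z = 0.89. Censoring two of the 20 progressors one month early, with events evenly spaced over months 3-6, gives z from 1.23 to 1.38. It crosses 1.28 for only 39% of the possible pairs.

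Nor is the 8.3 count inflated by censoring, since a censored man is not credited. Type I error under that count stays near 13% at every f.

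Finally, scoring an open-label stop as an event moves the endpoint towards treatment failure, while the 50% and 66% benchmarks were set for PSA-progression-free survival. That is a fair cost. Fuller PSA observation to month 6 would keep the endpoint as defined. It would not help where new therapy has already lowered PSA.

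What the objection does not supply is a scoring rule. Nor does it close the six-month interval without a scheduled PSA.

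**Conclusion.** The concern holds in conditional form. Sections 3.1 and 4.6 differ on stop reasons, and no rule scores a man who stops for lack of efficacy or starts new prostate-cancer therapy before PSA progression. The visit plan can leave his six-month status unresolved even when followed exactly.

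If that happens to about one man in 46, the 8.4 test exceeds its 10% level (about 13%). At two to three men it is 17-19%, and at four to five 29-35%. Futility stopping under 8.9 becomes less likely in step.

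These sizes rest on the assumed f, on exponential times, and on progression being truly unobserved. They shrink to nothing for men whose progression the end-of-treatment PSA captures. For censored men the bias affects 8.4 and 8.9, not the 8.3 count, so the two final rules can treat the same man differently. This should be settled before the interim analysis; confidence is medium because the documents give no rate.

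**What to change.** In 8.3, 8.4, 8.9 and 8.10, state that stopping for lack of efficacy, or starting new prostate-cancer therapy, before documented PSA progression counts as a failure, with the event on the stop or start date, at both the interim and final analyses. Report the PCWG3-only analysis, with these men censored, as a sensitivity analysis. Reconcile the stop reasons in 3.1 and 4.6; which list is right is for the sponsor.

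The cost is a sentence in the statistical section, the dates and reasons for stopping and for new therapy, and one extra analysis. The downside is that a few men who might not have met the PSA rule by month 6 count as failures. The estimate becomes slightly less favourable and the endpoint becomes a composite, which the report should say when comparing it with 50% and 66%.

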3.2 Study Completion

The study will reach study completion approximately 36 months from the time the study opens to accrual.

4 SUBJECT PARTICIPATION, DISCONTINUATION, AND WITHDRAWAL

Investigators must follow all MCW IRB requirements and policies regarding subject participation, found here:

<https://www.mcw.edu/HRPP/Policies-Procedures.htm>

4.1 Subject Status

Subject statuses throughout the trial are defined as follows:

- Prescreening: preconsent (subject considering trial or study staff considering a patient for the trial per institutional recruitment methods).
- Screening: the period after the consent, but prior to eligibility confirmation.
- Consented: consented, prior to eligibility confirmation.
- Eligible: the local investigator confirms all eligibility criteria apply.
- On study/enrolled: date eligibility is confirmed.
- On arm: date of enrollment.
- On treatment: first-day treatment was given to the last day treatment was given.
- Off treatment: the last day treatment was given.
- On follow-up: from the last day of treatment to the end of the follow-up period.
- Off study: follow-up period completed, with no additional data gathered.
- Withdrawn: subject fully withdraws consent (i.e., refuses ALL follow-up, even survival) or is taken off the study by the local principal investigator.

4.2 Prescreening and Screening Log

The MCW study principal investigator regularly reviews screen failure reasons to understand barriers to accrual and consider amending eligibility criteria. Screen failures are defined as participants who were considered for the trial to participate in the clinical trial with or without consent but are not subsequently assigned to the study intervention or enrolled in the study. MCWCC CTO will follow its SOPs regarding prescreening and screening tracking.

4.3 Consent

Investigators or their appropriate designees will identify potentially eligible subjects from their clinics, subject self-referrals, referrals from other clinicians, and/or other IRB-approved recruitment methods. No study conduct, including subject prescreening, can occur until after IRB approval.

A written signed informed consent form (ICF) and a Health Insurance Portability and Accountability Act (HIPAA) authorization must be obtained before any study-specific assessments are initiated. A signed ICF copy will be given to the subject and a copy will be filed in the medical record (per local IRB policies and SOPs). The original will be kept on file with the study records.

4.4 Screening Procedures

Refer to the study calendar of events.

Visit procedures that were performed as standard of care before consent (without the specific intent to make the subject eligible for the trial), may count toward screening tests and eligibility if they are within the screening window.

4.5 Biospecimen studies and procedures

Archived tissue samples will be requested and are required if available. Tumor and blood biomarkers to be evaluated to support the exploratory objectives of the study may be evaluated per study calendar. Biomarker assessments that may have the potential to identify patients likely to respond to treatment with investigational agents will be investigated to determine a patient's biomarker status and for possible correlation with efficacy endpoints.

All samples collected for biomarker analyses will be stored and analyzed at [name] and [name] laboratory and may be used for subsequent research relevant to evaluating biological and/or clinical response to pacritinib.

Quantitative fluorescence-based immunohistochemistry will be used to determine levels of nuclear localized Stat5 in prostate cancer cells, to provide pilot data to explore the hypothesis that high levels of nuclear localized Stat5 in cancer cells prior to Jak2-inhibitor treatment correlate with responsiveness to pacritinib treatment.

Specimens to be provided:

One H&E and five unstained sections from formalin-fixed, paraffin-embedded prostate cancer samples from before initiation of pacritinib treatment (biopsy or resected specimen) will be required if available. Surgical specimens would be preferred over biopsy specimens when available. All archived tissue samples available may be used, not just the most recent sample.

Blood (2x10ml EDTA tube) will be collected per calendar and processed as below. Plasma will be isolated for cell-free DNA extraction and exosome isolation. The cell-free DNA will be tested for genetic and epigenetic changes. The exosomes will be tested to quantify their microRNA contents. Correlative analyses will be performed to associate the genetic and epigenetic

changes with treatment responses. These analyses will include (but not limited to) Cox regression, Kaplan-Meir and area under the curve (AUC)

Blood will be stored in [name] laboratory. If a response is detected after the first 10 patients, a protocol amendment will occur to allow for analysis of blood specimens. .Tissue and blood will be sent to:

[name]'s laboratory,

[name], Medical College of Wisconsin,
[name]
(office [contact], [contact]; [contact])

Laboratory staff:

[name] (Research Scientist; [contact]; [contact]; [contact]);

[name] PhD (Research Scientist; office [contact]; [contact]; [contact])

Either [name] or laboratory staff can be contacted for any questions regarding specimen (tissue and blood) handling.

1. Biomarkers to be assessed include Signal Transducer and Activator of Transcription-5a/b (Stat5a/b) and will be correlated with response to treatment.
2. If adequate tissue is not available for all study biomarkers to be done, the patient would still qualify and be enrolled to the study.

Pathologic Evaluation and Handling of Tissue Specimens:

1. Tissue for analysis will be subject to routine pathological analysis. Routine hematoxylin and eosin (H&E) stain will be used for morphological analysis and for the determination of carcinoma diagnosis. The samples will be assessed by our GU pathologists.
2. One H&E slide and five unstained slides will be reserved for study labs/biomarkers and will be sent to [name] laboratory (suite C4960) at the Medical College of Wisconsin Translational and Biomedical Research Center (TBRC).
3. Cancer cell levels of Stat5a/b protein will be quantified on slides, using optimized fluorescence-based multiplexed immunohistochemical protocols.

Handling of Blood Specimens

1. Collect blood in 2x10ml K2EDTA venous blood collection tubes.
2. Gently invert sample(s) eight to 10 times and process within 30 minutes, but no longer than two hours after blood draw.
3. Centrifuge specimens at approximately 3000 rpm in a standard clinical centrifuge for 10 minutes at RT.
4. Being careful to not disturb the buffy coat, transfer the platelets-rich plasma to a 15-ml conical tube and spin again at 3000 rpm to separate platelets from platelets-poor plasma.
5. Transfer buffy coat layer into a 2-ml cryovial tube. Some red blood cell contamination is expected.
6. Once finished with the second spin, transfer platelets-poor plasma to 1-ml cryovial tubes, being careful not to disturb pellet.

7. Label all aliquots with study, patient ID, date/time of collection, timepoint, and specimen (i.e. PPP – platelet poor plasma, BC – buffy coat, PL - platelet).
8. Immediately freeze samples at -80°C.

